## **5. Study Process**

### **5.1 Medical treatment group**

Patients admitted to the medical treatment group after screening could receive electrocardiography and receive class I or class III AAD to restore or maintain sinus rhythm. The survey included variables that concern the baseline characteristics of patients, including risk factors, clinical history, cardiac diagnosis, electrocardiogram, echocardiography, laboratory blood tests, and treatments. All patients were symptomatic (functional NYHA class II–IV) and were treated according to contemporary clinical guidelines.

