## 5.2 Cryoballoon ablation group

### ➤ Pre-procedure

In addition to survey contents for medical treatment group, the Transesophageal echocardiography (TEE) was performed in all patients prior to the procedure. The echocardiographic parameters include left ventricular ejection fraction (LVEF), peak early trans-mitral inflow velocity/peak late mitral inflow velocity ratio (E/A), left atrial diameter (LAD), LV end-diastolic diameter (LVEDD), and LV mass. All recordings were performed and analyzed by the same investigator. In patients on vitamin K antagonists, anticoagulation was continued throughout the procedure, aiming at an international normalized ratio (INR) of 2-3. In patients treated with novel oral anticoagulants (NOACs), the drug was discontinued 12-24 hour prior to the procedure and re-initiated 6-hour post-ablation at half the regular dose, and then at full dose on the following day.

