Post-ablation, all patients had in-office Follow-up visit at discharge. A subset of patients reconsented for 1, 3, 6, and 12-month follow-up visits. On follow-up visits physical examination was performed, a 12-lead electrocardio gram (ECG) and 24-h Holter monitor were recorded, and medication changes were documented. In addition, regular telephone interviews were performed. Additional outpatient clinic visits were immediately initiated in cases of symptoms suggestive of recurrent arrhythmia. Repeat ablation was offered to the patient in cases of symptomatic AF/AT recurrence after the blanking period or symptomatic drug-refractory recurrent AF/AT within the blanking period that could not be managed without intervention. Furthermore, LVEF and the NYHA score were systematically evaluated at follow-up on TTE.

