## **6. Outcome Measures**

➤ **Primary Outcome Measures:**

(1) Treatment success at one year

Treatment success at 12 months after antiarrhythmic drug (AAD) initiation or ablation utilizing cryoballoon catheter measured by freedom from AF recurrence following a 3-month period after the index ablation or AAD initiation.

The primary outcome was time to first documented recurrence of symptomatic or asymptomatic atrial tachyarrhythmia (AF, atrial flutter, or atrial tachycardia)

(2) Rate of serious adverse events

Rate of complications and adverse events occurred during cryoballoon ablation and postoperative follow-up, including procedure-related complications such as bleeding, phrenic nerve palsy (PNP), cerebral embolism, pericardial effusion/tamponade, atriopharyngeal fistula, and all-cause mortality, re-hospitalization for HF, and the composite event of all-cause mortality or HF hospitalization.

➤ **Secondary Outcome Measures**

(1) Quality of life changes at 12 months measured by AF Quality of Life Survey (AFEQT)

The improvement in quality of life between baseline and 12 months after the index ablation procedure or AAD measured by AFEQT is evaluated.

(2) Quality of life changes at 12 months measured by 12-Item Short Form Survey (SF-12)

The improvement in quality of life between baseline and 12 months after the index ablation procedure or AAD measured by SF-12 is evaluated.

(3) Arrhythmia recurrence during blanking period (Time Frame: 3 months)

Atrial tachycardia recurrence rate during the blanking period is evaluated.

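### AFEQT and SF-12 change is an outcome in both groups, but no listed assessment names either questionnaire, and the only scheduled month-12 visit is for a re-consenting ablation subset

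*Combined protocol and SAP*

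**What the plan says.** Section 6 (Secondary Outcome Measures) defines the first quality-of-life outcome as follows: "The improvement in quality of life between baseline and 12 months after the index ablation procedure or AAD measured by AFEQT is evaluated". The second uses the same form: "The improvement in quality of life between baseline and 12 months after the index ablation procedure or AAD measured by SF-12 is evaluated". Both cover the two treatments and both are changes over 12 months.

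Section 5 describes what is collected.

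- **Baseline, drug group (Section 5.1).** The data collection covers "variables that concern the baseline characteristics of patients, including risk factors, clinical history, cardiac diagnosis, electrocardiogram, echocardiography, laboratory blood tests, and treatments".
- **Baseline, ablation group (Section 5.2, Pre-procedure).** The same content is carried over, with one addition: "In addition to survey contents for medical treatment group, the Transesophageal echocardiography (TEE) was performed in all patients prior to the procedure".
- **Follow-up, all ablation patients (Section 5.2, after Post-procedure).** "Post-ablation, all patients had in-office Follow-up visit at discharge".
- **Later visits (same place).** "A subset of patients reconsented for 1, 3, 6, and 12-month follow-up visits". Their content is given: "On follow-up visits physical examination was performed, a 12-lead electrocardio gram (ECG) and 24-h Holter monitor were recorded, and medication changes were documented". LVEF and NYHA class at follow-up are added, as are telephone interviews with no dates and no stated content.
- **Follow-up, drug group.** Section 5.1 sets out no visits after treatment starts.

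Section 7 gives general between-group tests. It has no analysis specific to quality-of-life change and no rule for missing scores.

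**The concern.** A change score needs two measurements on the same patient, and a comparison of change needs them in both groups. Section 6 asks for this, but Section 5 does not say at which contact, or in which patients, the questionnaires are completed. The word survey in Sections 5.1 and 5.2 refers to the baseline data collection and not to a quality-of-life instrument.

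Two things are at stake. First, allocation is not randomised (Section 2), so the groups may differ in quality of life at entry. A baseline score that is missed cannot be recovered once treatment has begun. Without it there is neither a change score nor a way to adjust for the starting difference. Second, the month-12 visit depends on a further agreement by the patient. Those who agree may differ in symptoms from those who do not, and Section 7 has nothing to deal with that selection.

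**Working it through.** The plan gives no figure to reproduce. The check sets what the outcomes need against what Section 5 lists.

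| Needed by Section 6 | Drug group | Ablation group |
|---|---|---|
| Baseline AFEQT and SF-12 | Not named in the Section 5.1 list | Not named; Section 5.1 content plus TEE |
| A scheduled month-12 visit | None described | Re-consented subset only |
| AFEQT and SF-12 at that visit | No visit described | Not named; examination, ECG, Holter, medication changes, with LVEF and NYHA at follow-up |
| Other contact that could carry them | None described | Telephone interviews, no dates or content |

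**Step 1: the questionnaires.** AFEQT and SF-12 appear only in Section 6. No baseline or follow-up list names either of them, in either group.

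**Step 2: the patients.** Suppose a site repairs step 1 by giving the questionnaires at the visits that are listed. At month 12 it then reaches only ablation patients who re-consented. No drug-group patient has a scheduled visit at which to be asked.

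**Step 3: the effect on the ablation mean.** Let p be the share of ablation patients who re-consent, R the mean change among them, and N the mean change among the others.

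- Mean for the whole ablation group = p × R + (1 − p) × N
- Mean observed at the visits = R
- Bias = R − [p × R + (1 − p) × N] = (1 − p) × (R − N)

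The documents give none of p, R and N. Taking p from 0.25 to 0.75 as an assumed range, the multiplier 1 − p runs from 0.75 to 0.25. So between a quarter and three quarters of any difference between returners and non-returners would pass into the observed mean. The sign of R − N is unknown: patients who feel better may be readier to return, or those who still have symptoms may be.

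**Step 4: the comparison.** If drug-group scores are obtained in some unscheduled way, the comparison carries the bias from step 3 and whatever selection acts on the drug side. If they are not obtained, there is nothing to compare with.

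**The case against.** The strongest case on the other side is that this is missing detail and not a contradiction. The Section 5.1 list is worded as open-ended. Section 6 belongs to the same document and names both instruments, both time points and both treatments, so a site that reads the whole plan knows that it must obtain the scores. This stands. A reader might infer that the outcomes cannot be derived at all, or that no patient would have a change score. The documents do not support that: they show that the collection is not scheduled, not that it did not happen.

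Nor is the re-consented visit shown to be the only contact at month 12. The telephone interviews in Section 5.2 are undated and are not confined to the subset, so some could fall then. This stands as well, but no questionnaire is listed for them and they appear only in the ablation text.

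A reader might also infer that the drug group has no contact at month 12. That is an inference from silence. The primary outcome is treatment success 12 months after ablation or AAD initiation, which implies that drug patients are followed to that point. What can be said is that Section 5.1 describes no schedule.

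Finally, the follow-up gaps also affect the primary outcome, where they matter more. That is true, but mending rhythm follow-up alone would not put the questionnaires into it.

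What none of this answers is the re-consent rule. It is stated, and following it produces a self-selected sample in one group only.

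**Conclusion.** The point holds as an inconsistency between Sections 5 and 6. Both quality-of-life outcomes require baseline and month-12 scores in both groups. No listed assessment names either questionnaire, and the only scheduled month-12 visit is for a re-consenting part of the ablation group. Had the questionnaires merely been left off the baseline list, this would be a matter of detail. The stated restriction of the later visits makes it a question of bias.

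Two of the three secondary outcomes are affected. No figure in points is supportable, since the size and selection of the subset are not given and the direction is unknown. The conclusion assumes that the questionnaires would be given at the listed visits, and that no separate assessment schedule outside this document provides for them. It should be put right, but as a matter of secondary outcomes.

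**What to change.** In Sections 5.1 and 5.2, list AFEQT and SF-12 at two points for every enrolled patient in both groups: before the first AAD dose or the index ablation, and at month 12 within a stated window. The month-12 assessment should not depend on belonging to the re-consented subset. Where a patient does not attend, the questionnaires are completed by telephone and the mode of completion is recorded. In Section 7, state how the change is analysed and how missing scores are handled.

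The cost is two questionnaires at two time points, a month-12 call to drug-group patients, and a mixture of telephone and in-person completion. No procedure is added. The consent text is not part of what can be read here, so whether it needs a change is for the sponsor to check.

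For patients already treated, a baseline score that was not taken cannot be supplied later. The report should then say who was assessed, when and by which mode, in each group.

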## **7. Statistical analysis**

(1) All statistical analyses were performed using SPSS version 22.0 software (SPSS, Chicago, IL, USA).

(2) All continuous variables were recorded as mean  $\pm$  standard deviation (SD). Categorical variables were presented as numbers or percentages. Between-group comparisons were performed using t-test, Mann–Whitney test, or Chi-square test. Fisher’s exact test was used when the observed value in any of the 2 $\times$ 2 contingency table cells was  $<5$ . Continuous variables were compared among groups using one-way analysis of variance or Kruskal–Wallis test.

(3) The effect of variables on the EF value was analyzed by univariate and multivariate logistic regression analyses. Baseline clinical features, medical history, and clinical and

laboratory parameters on admission were considered as candidate variables in the multivariate analysis.

(4) The association between the EF group and the outcomes was assessed using univariable and multivariable Cox analyses. Variables of relevant clinical interest considered as covariates were included in the multivariable model to identify the predictors for adverse outcomes according to EF category.

(5) A 2-sided p value less than 0.05 was considered as statistically significant.

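### Section 7 names no censoring-aware comparison of the treatment groups for primary outcome (1), so patients whose follow-up stops early can be counted as recurrence-free

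*Combined protocol and SAP*

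**What the plan says.** Section 6 gives primary outcome (1) in two forms. The first is success at 12 months, "measured by freedom from AF recurrence following a 3-month period after the index ablation or AAD initiation". The second is a time to event: "The primary outcome was time to first documented recurrence of symptomatic or asymptomatic atrial tachyarrhythmia (AF, atrial flutter, or atrial tachycardia". Section 6 does not say which form is analysed.

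Section 7, item (2), covers comparisons in general. For two groups: "Between-group comparisons were performed using t-test, Mann–Whitney test, or Chi-square test". For small cells, Fisher's "exact test was used when the observed value in any of the" 2×2 table is below 5. For several groups: "Continuous variables were compared among groups using one-way analysis of variance or Kruskal–Wallis test". Item (4) is the only place where a survival method appears: "The association between the EF group and the outcomes was assessed using univariable and multivariable Cox analyses". Treatment group is not named as a term in that model. Item (5) sets the threshold: "A 2-sided p value less than 0.05 was considered as statistically significant". Kaplan-Meier, log-rank, a censoring rule and a missing-data rule are not mentioned.

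On follow-up, Section 5.2 (Post-procedure) says of the ablation group: "A subset of patients reconsented for 1, 3, 6, and 12-month follow-up visits". ECG and 24-hour Holter are recorded at those visits. The same paragraph adds telephone interviews and extra clinic visits when symptoms suggest recurrence. Section 5.1 gives no follow-up schedule for the medical group.

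**The concern.** Section 1 makes ablation against medical therapy the study's comparison. For that comparison on a time-to-event outcome, the plan offers only tests that cannot use a patient observed for part of the year. If the outcome is reduced to a proportion, each patient who leaves without a recorded recurrence must be counted as a success, counted as a failure or dropped, and the plan does not say which.

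Counting them as successes makes the less-observed group look better, whatever the treatment does. This is separate from confounding by non-random allocation: it would distort a perfectly balanced comparison too. Incomplete observation is foreseeable from Sections 5.1 and 5.2. Because asymptomatic recurrence counts as an event, telephone contact and symptom-driven visits cannot fully replace scheduled recordings.

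**Working it through.** The documents give no event rate, dropout rate, group split or power statement, so there is no figure of the plan's own to reproduce. What follows is an illustration.

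**Inputs from the documents:** 200 patients in total (Section 2); two-sided 0.05 (Section 7, item 5); 12 months less a 3-month blanking period, so 9 months at risk (Section 6).

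**Assumptions:** 100 per group; the same true recurrence p in both groups (40% or 50% over the 9 months); constant hazards; loss unrelated to recurrence; early stoppers without a recorded recurrence counted as recurrence-free.

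**Gradual loss.** Let d be the proportion whose follow-up would end before month 12 if they had no recurrence. Then

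- recurrence hazard h = −ln(1 − p)/9
- loss hazard c = −ln(1 − d)/9
- crude observed recurrence = h/(h + c) × [1 − exp(−9(h + c))]

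Example with p = 0.40 and d = 0.20: h = 0.0568 and c = 0.0248 per month. Then exp(−9(h + c)) = 0.60 × 0.80 = 0.48, and crude recurrence = 0.0568/0.0816 × 0.52 = 0.362. A fully observed group shows 0.400. The treatments are identical, yet the crude rates differ by 3.8 points.

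**Upper bound.** If the lost patients are never observed while at risk, crude recurrence = p(1 − d), here 0.40 × 0.80 = 0.320.

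False-positive rates come from exact binomial enumeration of the uncorrected chi-square test, 100 v 100, with no loss in the other group:

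| Loss | Crude recurrence, gradual loss (p = 40% / 50%) | Chi-square error, gradual loss | Chi-square error, upper bound |
|---|---|---|---|
| 20% v 0% | 36.2% / 45.4% | 9% / 11% | 22% / 31% |
| 30% v 0% | 34.2% / 42.9% | 14% / 18% | 43% / 59% |
| 50% v 0% | 29.7% / 37.5% | 33% / 44% | 88% / 96% |

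A log-rank test on the same gradual-loss scenarios, simulated, rejects about 5% of the time in each.

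**Loss in both groups.** With gradual loss of 40% v 10% and p = 40%, crude recurrence is 32.0% v 38.1% and the error is about 15%. With equal loss of 20%, the error stays near 5%, but success is overstated in both groups: by 3.8 points (40.0% − 36.2%) to 4.6 points (50.0% − 45.4%) under gradual loss, and by 8 to 10 points at the upper bound.

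**A real effect can also be hidden.** With true recurrence of 30% v 50% and gradual loss of 10% v 40%, the crude rates are 28.6% v 40.3%. Chi-square power is then about 41%, against 79% for log-rank. Without loss, both have about 84%.

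**The case against.** Item (2) is a generic paragraph. It never assigns the chi-square test to primary outcome (1), and nothing in the documents says that unobserved patients count as recurrence-free; dropping them is equally possible, and if loss is random that keeps the error near 5%. For a 12-month yes/no outcome known in every patient, chi-square is legitimate, and Section 6 does word the outcome that way. All of this stands. A reader might infer that the plan prescribes a chi-square test with lost patients scored as successes. The text supports only that it leaves this open.

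A reader might also take 22–96% as the expected error. Those figures need the lost patients to be unobserved for the whole at-risk period, with no loss at all in the other group. The documents do not say that patients outside the re-consenting subset had no recordings: telephone interviews and symptom-triggered visits could still lead to one. Nor do they show complete follow-up in either group. Hence the gradual-loss figures lead, the others are an upper bound, and the direction of any bias is unknown.

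Finally, a survival method does not repair missing observation. A patient with no recording after discharge, censored at the last recording, leaves before blanking ends and contributes nothing, which amounts to being dropped. If loss depends on rhythm, as symptom-triggered visits make plausible, log-rank is biased too. This stands, and it limits what the fix can claim.

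What does not stand is that the existing Cox analysis covers the gap. Treatment might be among the covariates in item (4), but the text does not say so and names EF group as the exposure. A 12-month proportion would in any case still need a rule for patients not followed to month 12, and there is none.

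**Conclusion.** The point holds as a gap in specification: no censoring-aware comparison of the treatment groups is named for primary outcome (1), its two wordings are not reconciled, and incomplete, possibly unequal follow-up is foreseeable. If early stoppers are counted as recurrence-free and loss is gradual and confined to one group, the nominal 5% error becomes 9–11%, 14–18% or 33–44% at 20%, 30% or 50% loss. Equal loss leaves the error near 5% but overstates both success rates. Every recurrence rate, loss rate and group size here is assumed.

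Severity: should fix. The gap touches the primary efficacy comparison, but the harm depends on counting choices that the plan has not made, and part of the problem is ascertainment, which no choice of test can cure.

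**What to change.** In Sections 6 and 7:

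- State that the time-to-event version of primary outcome (1) is primary.
- Compare treatment groups by Kaplan-Meier and log-rank, with a Cox model containing treatment group and baseline covariates already collected. Adjustment is needed because allocation is not randomized.
- Start the clock at the end of the 3-month blanking period.
- Censor each patient at the last rhythm recording, not at the last telephone contact.
- Report 12-month success as the Kaplan-Meier estimate with a 95% confidence interval.
- Report, by group, how many patients have any rhythm recording after blanking, and state that censoring does not correct loss related to rhythm.

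The cost is mainly wording: item (4) already plans Cox analyses. The dates of rhythm recordings have to be available in both groups, including the medical group, for which Section 5.1 sets no schedule. The reported success rate may come out slightly less favourable and less precise.

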### 2. Study Design

Study Type	Interventional (Clinical Trial)
Estimated Enrollment:	200 participants
Allocation:	No-Randomized
Intervention Model:	Parallel Assignment
Primary Purpose:	Treatment
Estimated Study Start Date:	May 1,2022
Estimated Primary Completion Date:	December 31, 2023
Estimated Study Completion Date:	June 1, 2024

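### The switch to Fisher's exact test is tied to observed rather than expected cell counts; a minor fault that costs at most about 8 points of power at an assumed 100:100 split, and only if the chi-square is uncorrected

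*Combined protocol and SAP*

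**What the plan says.** Section 7(2) of the combined protocol and SAP gives the tests for comparing groups: "Between-group comparisons were performed using t-test, Mann–Whitney test, or Chi-square test". For small counts it adds that Fisher's "exact test was used when the observed value in any of the" four cells was below 5. No criterion based on expected counts appears anywhere, and the plan does not say whether the chi-square is continuity-corrected. Section 7(5) sets the significance level: "A 2-sided p value less than 0.05 was considered as statistically significant".

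The outcome most exposed to small cells is the second primary outcome in section 6, "Rate of serious adverse events". It covers procedural complications, death and heart-failure rehospitalisation. Section 7(2) is the only written method for comparing such proportions between groups.

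Section 2 plans "200 participants" with allocation described as "No-Randomized". It gives no group ratio, and no event rates, power or sample-size derivation are given anywhere.

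**The concern.** The chi-square approximation is judged by the counts expected under the null hypothesis, which depend only on the table margins. A small observed count in one group beside a larger one in the other does not make the approximation poor; it may simply be the difference between the groups. A rule based on observed counts can therefore go wrong in two ways:

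- It can send a table to the more conservative Fisher test although every expected count is at least 5. A true difference in a low-count outcome then becomes harder to detect.
- When the groups are unequal in size, it can keep chi-square although an expected count is below 5.

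What is at stake is which p-value is reported for low-count components of a primary outcome.

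**Working it through.** **Inputs.** From the plan: total N = 200, two-sided alpha 0.05, Fisher if any observed cell is below 5, otherwise chi-square. Assumed: 100 per group, uncorrected Pearson chi-square, and a range of event rates. The plan states no power figure, so there is none to reproduce.

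**Method.** Every 2×2 table is enumerated with independent binomial counts in the two groups. The written rule (Fisher if any *observed* cell < 5) is compared with the alternative (Fisher if any *expected* cell < 5). Both use Pearson otherwise.

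**Step 1: where the rules differ at 100:100.** With m events in total, each group's expected event count is 100m/200 = m/2. This is at least 5 once m ≥ 10. At low event rates the rules therefore choose different tests when the total is 10 or more and one group has 4 or fewer.

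**Step 2: which of those tables change the verdict.** Pearson X² = d² × Σ(1/E), where d is observed minus expected and E the expected counts.

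- 2 v 9: E = 5.5 and 94.5, d = 3.5; X² = 12.25 × (2/5.5 + 2/94.5) = 4.71, p = 0.030. Fisher p = 0.058.
- 3 v 10: E = 6.5 and 93.5, d = 3.5; X² = 12.25 × (2/6.5 + 2/93.5) = 4.03, p = 0.045. Fisher p = 0.082.
- 4 v 12: E = 8 and 92, d = 4; X² = 16 × (2/8 + 2/92) = 4.35, p = 0.037. Fisher p = 0.065.

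These are the only low-count tables at 100:100 where the two rules fall on different sides of 0.05 (in either direction between groups).

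**Step 3: power.** The loss is the probability of landing on those tables. At 3% v 10%, using binomial probabilities for 100 patients per group:

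- 2 v 9: 0.2252 × 0.1304 = 0.0294
- 3 v 10: 0.2275 × 0.1319 = 0.0300
- 4 v 12: 0.1706 × 0.0988 = 0.0169

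The sum is about 0.076; the mirror-image tables add almost nothing. This is the largest loss found at 100:100. Other scenarios:

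| Event rates | Written rule | Expected-count rule | Loss (points) |
|---|---|---|---|
| 3% v 10% | 43.8% | 51.5% | 7.6 |
| 2% v 10% | 59.2% | 66.0% | 6.9 |
| 3% v 12% | 63.8% | 70.3% | 6.5 |
| 1% v 8% | 56.8% | 59.9% | 3.1 |
| 5% v 15% | 65.9% | 68.2% | 2.3 |
| 1% v 5% | 19.4% | 20.1% | 0.7 |
| 1% v 3% | 3.4% | 3.4% | none |
| 10% v 20% | 51.7% | 51.8% | 0.1 or less |
| 30% v 50% | 83.2% | 83.2% | none |

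(Losses are from unrounded powers.)

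**Step 4: continuity correction.** The corrected p-values for 2 v 9, 3 v 10 and 4 v 12 are 0.063, 0.085 and 0.068, so none is significant under either rule. At 100:100 the written rule then has no loss anywhere and is slightly better: 42.3% v 39.6% at 3% v 10%, and 61.1% v 58.4% at 3% v 12%.

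**Step 5: unequal groups.** With uncorrected Pearson, the maximum loss over the splits scanned from 100:100 to 180:20 lay between 1.6 points (170:30) and 7.7 points (130:70). The opposite error also appears. At 150:50 with 5 events in each group, every observed cell is at least 5, but the smallest expected count is 50 × 10/200 = 2.5, so the plan keeps chi-square. The effect on size is slight: at 150:50 and common rates up to 10%, the largest type I error is 5.1% as written against 4.6% with the expected-count rule.

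**Step 6: size at 100:100.** At common event rates of 5%, 8% and 10%, actual size is 2.1%, 3.8% and 4.7% as written, and 3.3%, 5.1% and 5.2% with the expected-count rule.

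**The case against.** The strongest reply is that Fisher's test is valid at any cell count. Where the written rule over-uses it, the rule gives up some power but introduces no bias, and its size at 100:100 stays further below nominal at low event rates. That stands, and it is why this is a minor point.

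The size of the loss also rests on things the plan does not say. It needs uncorrected Pearson, a near-worst-case pair of rates and an assumed split; with continuity correction at 100:100 the sign reverses. That stands too.

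Three stronger readings are tempting and are not supported:

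- *That the second primary outcome as a whole loses about 8 points.* Several listed complications are procedural, and a drug group would be expected to have none. With 0 events in one group of 100, the verdicts never differ: totals below 10 go to Fisher under both rules, and 0 v 10 or more is significant under both. Only outcomes that can occur in both groups, within a narrow range of rates, are exposed.
- *That ejection-fraction subgroups would suffer more.* The loss can be larger in small comparisons (13.1 points at 50 v 50 with 5.5% v 19%). But the plan gives neither the number nor the size of the categories and describes no 2×2 treatment tests within them. Section 7(4) assigns the relation between EF group and outcomes to Cox models.
- *That the rule always errs towards caution.* With unequal groups it can err the other way, as Step 5 shows.

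**Conclusion.** The trigger in section 7(2) is mis-specified: it should refer to expected counts. With uncorrected Pearson and a 100:100 split, both assumed, the cost is at most about 8 points of power, typically 0 to 3 points when events are common or very rare, and three low-count tables on which the 0.05 verdict changes. With continuity correction at 100:100 there is no power loss. With unequal groups, which the non-randomised design allows, the rule can also retain chi-square below the usual expected-count threshold, with little effect on type I error in the splits examined. Only crude comparisons of proportions are touched; the Cox analyses do not depend on this rule. In a non-randomised comparison, a few points of power on an unadjusted test will not decide credibility, so the priority is minor.

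**What to change.** Replace the sentence in section 7(2) with: *Fisher's exact test is used when the expected count in any cell of the 2×2 table is <5; otherwise Pearson chi-square without continuity correction.* This corrects the trigger and settles the unstated choice on which the size of the effect depends.

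The change needs no new data or patients. Its one small downside is the slight excess over nominal size shown in Step 6 (5.1–5.2% at common rates of 8–10%, 100:100). It should be made before the outcome data are analysed, because changing the test after seeing a borderline p-value would not be credible.
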